1.3 Chronic migraine	
A. Headache (migraine-like or tension-type-like) on ≥ 15 days/month for > 3 months, and fulfilling criteria B and C	
B. Occurring in a patient who has had at least five attacks fulfilling criteria B to D for 1.1 Migraine without aura and/or criteria B and C for 1.2 Migraine with aura	
C. On ≥ 8 days/month for > 3 months, fulfilling any of the following: 1. criteria C and D for 1.1 Migraine without aura 2. criteria B and C for 1.2 Migraine with aura 3. believed by the patient to be migraine at onset and relieved by a triptan or ergot derivative	
D. Not better accounted for by another ICHD-3 diagnosis	

3.6.1 Migraine Day

The migraine day definition is based on the IHS guidelines¹ for controlled studies of preventive treatment of migraine in adults.

During the trial, a day with a headache can be here defined as a migraine day if the headache belongs to any subgroup of headaches.

(1) A headache lasts at least 30 minutes and meets the following two criteria:

- At least two of the following four characteristics:
 - unilateral location
 - pulsating quality
 - moderate or severe pain intensity
 - aggravation by or causing avoidance of routine physical activity
- During the headache the participant had at least one of the following:
 - nausea
 - vomiting
 - photophobia and phonophobia

(2) A headache lasts at least 30 minutes and where the participant had an aura with the headache

(3) A headache lasts at least 30 minutes and meets two of the following three criteria:

- lasting 4 hours
- At least two of the following four characteristics:
 - unilateral location
 - pulsating quality
 - moderate or severe pain intensity
 - aggravation by or causing avoidance of routine physical activity
- During the headache the participant had at least one of the following:
 - nausea
 - vomiting
 - photophobia and phonophobia

(4) A day with a headache that is successfully treated* with a migraine specific treatment, as classified in the master medication list.

(5) A day with an aura without a headache with medication taken

Data on characteristics of a headache will be collected in the eDiary for each day of the headache. For each headache it will be determined whether a headache is a migraine or a non-migraine headache based on the total headache duration and the pooled symptoms over all days of the headache. All days on which this headache occurs will then be classified as a migraine day if the headache qualifies as a migraine headache.

If a headache lasts ≥ 72 hours, the days will still be counted as *headache days* or *migraine days* as aligned with the IHS guidelines.¹

Further details on the definitions:

* If participants are taking acute migraine medication, the following questions are captured in the headache diary: “*Did you take any medications to treat this headache today?*” and “*Did at least one of the medications you took today successfully treat your headache?*” Only if both are affirmed will the treatment of the headache be considered “successful”.

For exploratory analyses, two alternative definitions of a migraine day will be applied:

- (1) a day will be qualified as a migraine day based on the symptoms and duration of the headaches occurring on that specific day only.
- (2) if a headache is lasting several days, all days on which this headache occurs will then be classified as a migraine day if the headache qualifies as a migraine using the approach number 1) for at least one of these days.

3.6.2 Headache Day

A headache day is defined as a day with a headache that lasts ≥ 30 minutes or that meets the definition of a migraine day.

Note: In case of a headache with start date/time and end date/time spanning multiple calendar days, all the calendar days overlapping with the ongoing headache (regardless of duration) will be counted as a headache day (or a migraine day if the headache qualifies as a migraine headache).

If a headache lasts ≥ 72 hours, the days will still be counted as *headache days* or *migraine days* as aligned with the IHS guidelines.

For the exploratory analyses corresponding to using the alternative definitions 1) and 2) for a migraine day as outlined in the previous section, a headache day is defined as a day on which the headache lasts ≥ 30 minutes on that specific day or that meets the definition of a migraine day.

3.7 Definition of a Reported eDiary Day and a Missing eDiary Day

A reported eDiary day is a day where at least one of the following pieces of information are available:

- A headache event is reported to take place and the participant has recorded the daily symptoms for at least one of the days spanned by this headache
- The headache eDiary has been completed, and it has been confirmed that no headaches happened on this day
- Aura without headache diary is reported with a taken medication

A missing eDiary day is defined as a day that is not a reported eDiary day.

3.8 Definition of Migraine Attack and Headache Episode

3.8.1 Migraine Attack

A migraine that fulfils the criteria for a migraine, is also referred to as a migraine attack. A migraine attack can last for a single day or for multiple days. Two migraine attacks are considered distinct, if they are split by a time gap where the participant had no headache at all. A time gap can be of any duration, i.e. two attacks are distinct as soon as there is a period of time of

any duration in between where the participant did not have a headache. An aura without headache with a taken medication is also considered a migraine attack.

3.8.2 Headache Episode

A non-migraine headache that lasts ≥ 30 minutes or a migraine headache, is also referred to as a headache episode. A headache episode can last for a single day or for multiple days. Two headache episodes are considered distinct, if they are split by a time gap where the participant had no headache at all.

3.9 Definition of Chronic Migraine and Medication Overuse Headache based on eDiary data

Participants who have a diagnosis of CM and MOH by IHS ICHD-3 guidelines at the Screening Visit and at the Baseline prior to the IMP will be randomized and dosed. Also, several endpoints are based on whether or not the participant fulfils the CM or MOH criteria during a specific post-baseline 4-week period using the following definition.

3.9.1 Definition of CM based on eDiary data

To evaluate whether a participant fulfils the CM criteria during a specific post-baseline 4-week period, we will use the eDiary data for that month (28-day period) and follow the steps below.

Step 1: Count number of monthly headache days.

If MHD ≥ 15 days in the reported month, then continue to Step 2.

Step 2: Count number of monthly migraine days

At least 8 monthly migraine days using definition of migraine day from [3.6.1](#) are needed for a participant to fulfil the CM criteria.

3.9.2 Definition of MOH during the trial

Panel 4 IHS ICHD-3 Guidelines for MOH

- A. Headache occurring on ≥ 15 days/month in a patient with a pre-existing headache disorder
- B. Regular overuse for >3 months of one or more drugs that can be taken for acute and/or symptomatic treatment of headache
- C. Not better accounted for by another ICHD-3 diagnosis

Regular overuse is defined either on:

- 10 days of use/month or more for >3 months of ergotamine, triptan, opioid (butorbital in US), or combination of analgesics
- 15 days of use/month or more for >3 months of non-opioid analgesics (paracetamol [acetaminophen], acetylsalicylic acid, NSAIDs)

In [Panel 4](#) above, the IHS ICHD-3 Guidelines for MOH are stated and used to confirm the MOH diagnosis at the screening visit.

During the trial, to evaluate whether a participant continues to overuse acute migraine medication, the eDiary data will be used for a specific post-baseline 4-week period (28-day period) only and the steps below will be followed:

Check acute migraine medication overuse in the reported month.

Count the number of days on which a medication was taken to treat a headache for each pre-defined acute migraine medication in the reported month (28-days period).

If the participant meets any of the following criteria in the reported month, the participant is considered as overusing acute migraine medication, used as “MOH” in the endpoint definitions. N is the number of monthly days.

- $N \geq 10$ days with either ergotamine, or $N \geq 10$ days with triptan
- $N \geq 10$ days with combination of two or more drug classes among ergotamine, triptan, opioid analgesic and non-opioid analgesics
- $N \geq 10$ days on which combination analgesics are taken.
- $N \geq 15$ days on which a non-opioid analgesic (paracetamol, acetylsalicylic acid, NSAIDs, analginum, antipyrine, tolfenamic acid) is taken. The overuse could be with a single non-opioid analgesic or with several of them.

4 Analysis Sets

The following analysis sets will be used to analyse and present the data:

- *all-participants-screened set (APSS)*
- *all-participants-randomized set (APRS)* – all randomized participants
- *all-participants-treated set (APTS)* – all participants in the APRS who received an infusion of the IMP in the Placebo-controlled Period
- *full-analysis set (FAS)* – all participants in the APTS who had a valid baseline assessment and at least one valid post-baseline 4-week assessment of MMDs in Weeks 1-12
- *all-participants-treated-open-label set (APTS-OL)* – all participants in the APRS who received an infusion of the IMP in the Open-label Period
- *all-participants-treated-follow-up set (APTS-FU)* - All participants in the APTS who are not in the APTS-OL, and who have data collected from the Safety Follow-up visit.

All data from the Placebo-controlled Period will be cleaned and the trial database for the Placebo-controlled Period will be locked when all participants have either completed or been withdrawn from the Placebo-controlled period. The participants and data will be classified into the analysis sets (APRS, APTS, and FAS) at a *Classification Meeting* held after the trial database for the Placebo-controlled Period has been released.

Data will be unblinded after the *Classification Meeting* for the sponsor and CRO functions involved in performing the analysis. All analyses specified in the SAP for data collected in the

Placebo-controlled Period will be performed. Sponsor and CRO functions that are in contact with the trial site staff, as well as clinical site staff and participants will remain blinded to individual participant treatment assignment through the end of the trial.

After all participants have completed the Open-label Period, the trial database for the full trial will be cleaned and locked. The participants and data will be classified into the analysis sets (APTS-OL and APTS-FU) according to these definitions. The defined population sets will be reviewed at a second *Classification Meeting* held after the full trial database has been released. The CTR will be issued after the end of the full trial completion.

Unless otherwise specified, the FAS will be used for all efficacy analyses in the Placebo-controlled Period, and the APTS will be used for all safety analyses in the Placebo-controlled Period, while the APTS-OL will be used for the safety and efficacy analysis of the Open-label Period. Relevant safety outputs for data collected at the Safety Follow-up visit for the APTS-FU will be listed.

5 Descriptive Statistics

In general, summary statistics (n, arithmetic mean, standard deviation [SD], median, lower and upper quartiles, minimum and maximum values) will be presented for continuous variables and counts and, if relevant, percentages will be presented for categorial variables.

Mean, median and confidence intervals (CIs) will be presented with one more decimal place than the individual values. SD will be presented with two more decimal places than the individual values. Minimum and maximum will be presented with the same number of decimal places as the individual values. P-values will be presented with four decimal places, ratios with three decimal places and test statistics with two decimal places. Percentages will have one decimal place.

Unless otherwise specified, data listings for the Placebo-controlled Period will include site, treatment group, participant screening number, sex, age, and race. For the Open-label Period, the listings will include treatment sequence in the Open-label Period in addition to the variables included in listings for the Placebo-controlled Period.

6 Participant Disposition

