1.1 Background

1.1.1 Overview

Migraine is a disabling disorder characterised by headache and often accompanied by nausea, vomiting, photophobia, and phonophobia.¹ Migraine is one of the most prevalent neurological disease for which medical treatment is sought, and worldwide, is considered the leading cause of disability for people under the age of 50 and second leading cause of disability worldwide.^{2,3}

MOH is the development of a new type of headache, or significant worsening of pre-existing headache, resulting from frequent and excessive intake of medications for the acute treatment of headache¹. MOH prevalence is estimated at 1% to 2% worldwide but varies from country to country (range 0.5% to 7%). Acute medications (for treatment of a migraine / headache once it begins) involved in MOH vary with country and over time.^{4,5} MOH is defined as the combination of chronic headache and overuse of analgesics and/or acute migraine medication (use of paracetamol and NSAID ≥ 15 days a month, or triptans, ergotamine, opioids, combination-analgesics, or any combination of drug classes ≥ 10 days a month). In fact, medication overuse is considered the most central factor for chronification of migraine, and 40% to 70% of patients with CM also fulfil the diagnostic criteria for MOH.

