6.7 Post-study Access to IMP(s)

Patients in the study will have access to appropriate medical care after they complete or withdraw from the study.

7 Concomitant Medication

Concomitant medication is any medication other than the IMP and that is taken during the study, up until the Safety Follow-up Contact, including during the screening period.

The concomitant medications that are disallowed or allowed with restrictions during the study are summarized in [Appendix II](#). Some of the restrictions apply up until the EoS Visit (Week 24) after which the investigator should continue to treat the patient as required by the patient's clinical condition. The restriction for use of mAb targeting the CGRP pathway must also be applied during the safety follow-up period.

Acute medication for treatment of migraine (triptans, ergotamine, combination of non-opioid analgesics, individual non-opioid analgesics, opioid analgesics, and NSAIDs) is allowed for the entire duration of the study and will be collected in the eCRF and the eDiary.

Investigators must ensure the patients are informed to which class of medication(s) their acute treatment(s) belong to.

Details of all concomitant medication (prescription and OTC), traditional herbal medicines, non-pharmacological interventions, and vitamin and mineral supplements for the treatment of migraine taken <3 months prior to the Screening Visit must be recorded in the eCRF at the Screening Visit. Any changes (including reason for changes) in these therapies must be recorded at each subsequent visit.

Details of all migraine preventive medications including treatment failures (prescription and OTC) taken within 5 years prior to the Screening Visit must be recorded in the eCRF at the Screening Visit.

For any concomitant medication, traditional herbal medicines, non-pharmacological interventions, and vitamin and mineral supplements for which the dose has been increased due to worsening of a concurrent disorder after enrolment in the study, the worsening of the disorder must be recorded as an adverse event. For any of these therapies initiated due to a new disorder after enrolment in the study, the disorder must be recorded as an adverse event.

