1.3 Chronic migraine	
A. Headache (migraine-like or tension-type-like) on ≥ 15 days/month for > 3 months, and fulfilling criteria B and C	
B. Occurring in a patient who has had at least five attacks fulfilling criteria B to D for 1.1 Migraine without aura and/or criteria B and C for 1.2 Migraine with aura	
C. On ≥ 8 days/month for > 3 months, fulfilling any of the following: 1. criteria C and D for 1.1 Migraine without aura 2. criteria B and C for 1.2 Migraine with aura 3. believed by the patient to be migraine at onset and relieved by a triptan or ergot derivative	
D. Not better accounted for by another ICHD-3 diagnosis.	

For the diagnosis of MOH, the investigator will make the diagnosis by using the IHS ICHD-3 guidelines¹ listed in **Panel 5**.

Panel 5 IHS ICHD-3 Guidelines for MOH

A. Headache occurring on ≥ 15 days/month in a patient with a pre-existing headache disorder

B. Regular overuse for >3 months of one or more drugs that can be taken for acute and/or symptomatic treatment of headache

C. Not better accounted for by another ICHD-3 diagnosis

Regular overuse is defined either on:

- 10 days of use/month for >3 months of ergotamine, triptan, opioid (butorbital in US), or combination of analgesics
- 15 days of use/month for >3 months of non-opioid analgesics (paracetamol [acetaminophen], acetylsalicylic acid, NSAIDs)

In order to meet the eligibility with regards to MOH for the study, a patient has to have headache on ≥ 15 days/month for each month within the past 3 months prior to the Screening Visit and have regular overuse of one or more drugs that can be taken for acute and/or symptomatic treatment of headache, for >3 months.

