15.1.4 Migraines/Headaches with Severe Pain Intensity and Migraine Attacks/Headache Episodes

The percentage of migraines/headaches with severe pain intensity is derived based on the derived number of monthly migraine attacks and headache episodes.

Migraine attack and headache episodes are defined in the Section 3.8. Headache severity is collected on a 3-point scale, Mild, Moderate and Severe. Migraines and headaches with severe pain intensity on at least one day are defined as migraine attacks/headache episodes with a reported severity of “Severe”.

The following describes the derivation of number of monthly migraine attacks. The derivation of monthly headache episodes follows the same principles.

The derivation of the number of monthly migraine attacks will follow the imputation rules described in Section 15.1.1 for MMDs, replacing *Reported Migraine Days* with *Reported Migraine Attacks* everywhere. As an example, the number of monthly migraine attacks for a participant with 14 days or more of eDiary reporting in a 4-week period will be derived as:

$$28 * (\text{Reported Migraine Attacks}/\text{Reported eDiary Days})$$

The number of monthly migraines with severe pain intensity is derived in the same way using only migraine attacks with a reported severity of “Severe”.

The percentage of migraines and headaches with severe pain intensity is then calculated as the percentage of migraine attacks/headache episodes with severe pain intensity out of the number of migraine attacks/headache episodes. Participants with no migraine attacks/headache episodes are included with a rate of 0.

15.1.5 Monthly Days with Acute Migraine Medication Usage and MMDs with Acute Migraine Medication Usage

In the aura without headache and headache diaries, as well as the evening diary, participants are asked each day to fill out whether they used any of the following medications during that day: ergotamine, triptan, non-opioid analgesic, barbiturates, opioid, or combination analgesic. A day where the participant answers that they took any of those in the diary is considered a day with use of acute migraine medication.

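### The SAP's on-trial overuse rule (3.9.2) has no criterion for an opioid used alone, so single-ingredient opioid use on 10 to 28 days is scored as not MOH, contrary to Panel 4 in the same section

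*SAP*

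**What the plan says.** Panel 4 in SAP 3.9.2 sets out the ICHD-3 definition of MOH. Criterion A requires headache on 15 or more "days/month in a patient with a pre-existing headache disorder". Regular overuse is then "10 days of use/month or more for >3 months of ergotamine, triptan, opioid (butorbital in US), or combination of analgesics", or 15 days for non-opioid analgesics. Protocol 9.1.2, Panel 5, gives the same list: "10 days of use/month for >3 months of ergotamine, triptan, opioid (butorbital in US), or combination of analgesics". Protocol 1.1.1 also names opioids separately from mixed use: "or triptans, ergotamine, opioids, combination-analgesics, or any combination of drug classes". Protocol 16.8.4 ties the CM-nor-MOH endpoint to the protocol's diagnostic panels and leaves further detail to the SAP.

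For post-baseline periods, SAP 3.9.2 replaces Panel 4 with a count of medication days in one 28-day period. A participant is an overuser if any of four criteria is met:

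1. ergotamine on 10 or more days, or a triptan on 10 or more days;
2. 10 or more "days with combination of two or more drug classes among ergotamine, triptan, opioid analgesic and non-opioid analgesics";
3. combination analgesics on 10 or more days;
4. non-opioid analgesics on 15 or more days.

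Opioid use can occur and can be seen in the data. Protocol chapter 7 states that acute medication including "individual non-opioid analgesics, opioid analgesics, and NSAIDs) is allowed for the entire duration of the study". Protocol Appendix II allows prescription opiates, single-ingredient products included, subject to a regimen stable for 12 weeks before screening. SAP 15.1.5 records the daily classes as "ergotamine, triptan, non-opioid analgesic, barbiturates, opioid, or combination analgesic".

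**The concern.** The four criteria carry over every class named in Panel 4 except one. Opioid survives only inside the mixed-class criterion, so an opioid taken alone can never trigger the rule. Neither SAP 15.1.6 nor chapter 18, which lists changes from the protocol, gives a reason.

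The flag feeds the MOH-only secondary endpoints (SAP 11.5), the CM-nor-MOH key secondary endpoints at steps 5 and 6 of the hierarchy (SAP 11.2), and the Weeks 13-24 version of the composite. The misclassification runs one way: a participant who is still overusing an opioid is recorded as free of MOH.

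**Working it through.** **Single classes.** Apply the four criteria to a participant who uses one class only, on 0 to 28 days.

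| Class used alone | First day count flagged, SAP on-trial rule | Panel 4 day threshold |
|---|---|---|
| Ergotamine | 10 | 10 |
| Triptan | 10 | 10 |
| Combination analgesic | 10 | 10 |
| Non-opioid analgesic | 15 | 15 |
| Opioid | never | 10 |

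The two columns differ only for the opioid, at 10 to 28 days. That is 28 − 10 + 1 = 19 day counts, of which the SAP rule flags 0. With an added criterion of 10 or more opioid days it flags all 19.

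**Opioid plus a little triptan.** Take an opioid on 10-28 days and a triptan on 1-9 days: 19 × 9 = 171 pairs. If criterion 2 means days on which both classes were taken, the overlap is at most 9 and 0 of 171 are flagged. If it means days pooled over classes, 171 of 171 are flagged. With the added criterion, 171 of 171 are flagged either way. This shows that criterion 2 is ambiguous, not how many participants are affected.

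**Which endpoints go wrong.** CM under SAP 3.9.1 requires at least 15 monthly headache days (MHD) and "At least 8 monthly migraine days using definition of migraine day from" Section 3.6.1. The composite is a success only if neither CM nor MOH is fulfilled (SAP 15.1.6). For an opioid-only overuser in one 28-day period:

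| Cell | CM | Composite as written | Composite against Panel 4 with criterion A | MOH-only as written | MOH-only against Panel 4 with criterion A |
|---|---|---|---|---|---|
| A: MHD ≥15, MMD ≥8 | met | failure | correct | success | wrong |
| B: MHD ≥15, MMD <8 | not met | success | wrong | success | wrong |
| C: MHD <15 | not met | success | correct | success | correct |

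The on-trial rule does not apply criterion A to any class. In cell C an opioid-only overuser is therefore treated differently from a triptan-only overuser, even though Panel 4 itself would not call either one MOH.

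**Size.** One participant is 1/285 = 0.35 percentage points of an arm as randomized, or 1/270 = 0.37 points of the 270 per arm expected to contribute. Beyond that, every input is an assumption:

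- opioid-only share of an arm: 1%, 3% or 5%;
- still overusing in the period: 30-70%;
- of those, in cell B: 5-10%;
- of those, with MHD ≥15 (cells A and B): 35-70%.

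Excess success rate per arm against Panel 4 with criterion A, for one 28-day period:

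- Composite = share × (0.3 × 0.05 to 0.7 × 0.10) = 0.02-0.07, 0.05-0.21 or 0.08-0.35 points. The upper ends are 0.2, 0.6 and 1.0 participants of 285.
- MOH-only = share × (0.3 × 0.35 to 0.7 × 0.70) = 0.11-0.49, 0.32-1.47 or 0.53-2.45 points.

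Step 6 combines all available periods, so these one-period figures do not carry over to Weeks 1-12.

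**The case against.** The strongest defence is that the on-trial rule is openly a simplification. It uses one 28-day period instead of more than 3 months and drops criterion A, and the protocol leaves the detail to the SAP. That explains the window and the missing headache count. It does not explain leaving out one drug class when the others are carried over.

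Two limits do stand. Combination analgesics are not defined in 3.9.2, so a fixed combination containing an opioid may be caught by criterion 3; only single-ingredient opioids clearly escape. Opioid use is also subject to the stable-regimen condition in Appendix II, which may keep the group small.

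Four stronger readings are tempting, and the documents do not support them.

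- A reader might score the composite on overuse alone, without criterion A. Assuming 40-70% of these participants are without CM, that gives share × (0.3 × 0.4 to 0.7 × 0.7), or 0.12-2.45 points across the three shares. It measures how far the rate would fall if the opioid criterion were added (cells B and C), on assumed inputs. It is not the error against Panel 4, and it mixes Panel 4's opioid threshold with a rule that omits Panel 4's headache count.
- A reader might infer that baseline status or eligibility is also wrong, because SAP 11.4.2 mentions a check at Baseline. That is one reading only. SAP 3.9 confines the definition to post-baseline periods, 3.9.2 uses Panel 4 at screening, and the logistic model contains no baseline MOH term.
- A reader might infer that nothing planned would reveal the problem. SAP Table 4 lists no sensitivity analysis for this endpoint, and 11.4.5 varies only the migraine-day definition. But SAP 7.2 (acute treatment types during screening, opioids named) and 8.2 (participants per medication type per 4-week interval) would bound the number of opioid users. They would not re-derive the endpoint.
- A reader might infer a false-positive risk. The same rule applies in both arms, so type I error is not inflated.

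**Conclusion.** The gap is certain and its size is not. As written, single-ingredient opioid-only use on 10-28 days of a 28-day period is scored as not MOH, against the SAP's own Panel 4 and Protocol Panel 5, with no stated reason.

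The MOH-only endpoints, which lie outside the testing hierarchy, are affected directly. Steps 5 and 6 are affected only when CM is not met and, against Panel 4 with criterion A, only in cell B.

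The number affected cannot be derived from the documents and is probably small. Under the assumed ranges, the one-period composite error is at most about one participant per arm. The primary endpoint is not affected, and no loss of power is claimed. This lies between a minor correction and one that should be made: the effect is likely slight, but a hierarchically tested endpoint named for the ICHD-3 criteria should count a class those criteria name.

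**What to change.** Add a fifth criterion to SAP 3.9.2: N ≥ 10 days on which an opioid analgesic is taken. This matches Panel 4's day threshold and resolves the mixed opioid-triptan cases under either reading of criterion 2.

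SAP version 3.0 is described as issued before unblinding, so timing matters. If the placebo-controlled data are already unblinded, keep the pre-specified derivation as the main analysis and report the corrected one as a disclosed sensitivity analysis for steps 5 and 6 and the MOH-only endpoints.

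While the section is open, it would help to define combination analgesics and say how barbiturates are classed, since SAP 15.1.5 records them and no criterion names them. These are clarifications, not errors.

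The cost is one bullet and one line of derivation code, or one extra analysis, using data already in the eDiary. The downside is that an added criterion can only leave response rates unchanged or lower them slightly, in either arm.

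### The SAP's multi-class overuse criterion omits combination analgesics and barbiturates and does not say whether days are counted same-day or cumulatively, so some mixed use on 10 or more days is scored free of MOH

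*SAP*

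**What the plan says.** SAP 3.9.2 derives on-trial MOH status from eDiary medication days in one 28-day period. The counting step is "Count the number of days on which a medication was taken to treat a headache for each pre-defined acute migraine medication". A participant is an overuser on meeting any one of these criteria:

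- ergotamine on at least 10 days, or triptan on at least 10 days;
- at least 10 "days with combination of two or more drug classes among ergotamine, triptan, opioid analgesic and non-opioid analgesics";
- combination analgesics on at least 10 days;
- at least 15 "days on which a non-opioid analgesic (paracetamol, acetylsalicylic acid, NSAIDs, analginum, antipyrine, tolfenamic acid) is taken".

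SAP 15.1.5 lists the classes the eDiary collects: "ergotamine, triptan, non-opioid analgesic, barbiturates, opioid, or combination analgesic". Protocol 1.1.1 sets the 10-day threshold for "triptans, ergotamine, opioids, combination-analgesics, or any combination of drug classes", and 15 days for paracetamol and NSAIDs. Panel 4 (SAP 3.9.2) and Panel 5 (Protocol 9.1.2) put opioids among the 10-day classes and contain no multi-class rule.

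Under SAP 15.1.6 the composite endpoint is a success only if neither CM nor MOH is fulfilled. It is tested at Steps 5 and 6 of the hierarchy (SAP 11.2). MOH alone is a secondary endpoint outside the hierarchy (SAP 11.5).

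**The concern.** Two things are wrong with the multi-class criterion. First, its class list is shorter than the list of classes collected. Combination analgesics count only in their own criterion, and barbiturates count nowhere. Two participants with the same number of treated days can then get opposite status only because one of them mixed classes.

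Second, the wording does not say whether the two classes must be taken on the same day or whether days are added across classes. The counting step works medication by medication and gives no rule for adding. Two competent programmers could derive different values of a key secondary endpoint.

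Nothing planned would reveal either problem. SAP Table 4 gives no sensitivity analysis for the two binary key secondary endpoints. The exploratory repeats in SAP 11.4.5 vary the migraine-day definition and not the overuse rule. SAP 18 does not list the narrower class set as a change from the protocol.

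**Working it through.** The documents' only computed design figure is the primary-endpoint sample size. It reproduces: 2 × 6.2² × (1.96 + 0.84)² / 1.5² gives 269 per arm, power at 270 is 80.3%, and 270/0.95 rounds up to 285. It is not at issue here. The plan gives no success rates for the MOH endpoints.

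**Status under the criteria as written.** Take use of two classes on separate days within 28 days. The single-class criteria allow at most 9 days each for triptan, ergotamine and combination analgesics, and 14 for non-opioids. No single-class criterion limits opioids or barbiturates. Same-day reading: count days with at least two listed classes. Cumulative reading: count distinct days with any listed class, if at least two listed classes were used in the period. The table gives the largest total of treated days still scored free of MOH.

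| Pair | Same-day | Cumulative | Cumulative, all six classes |
|---|---|---|---|
| Triptan + combination analgesic | 9 + 9 = 18 | 18 | 9 |
| Non-opioid + combination analgesic | 14 + 9 = 23 | 23 | 9 |
| Triptan + barbiturate | 9 + 19 = 28 | 28 | 9 |
| Triptan + ergotamine | 9 + 9 = 18 | 9 | 9 |
| Triptan + non-opioid | 9 + 14 = 23 | 9 | 9 |
| Triptan + opioid | 9 + 19 = 28 | 9 | 9 |

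The first three rows do not depend on the reading; the last three do. Opioid-only use on all 28 days also meets no criterion, although Panel 4 sets opioids at 10 days.

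**When this reaches Steps 5 and 6.** CM is fulfilled at 15 or more headache days with 8 or more migraine days (SAP 3.9.1). Each medication day is a day on which a headache was treated, so treated days are roughly a lower bound for headache days.

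- At 18 or 23 treated days, headache days are about 15 or more. CM is then avoided only with fewer than 8 migraine days. A headache day successfully treated with a migraine-specific drug is itself a migraine day (SAP 3.6.1), so 9 successful triptan days already exceed 8. Most such participants fail the composite on CM whatever their MOH status.
- At 10 to 14 treated days, headache days can be 10 to 14 and CM is not fulfilled. The overuse rule then decides. With 13 headache days, 12 triptan days is a composite failure, while 6 triptan plus 6 combination-analgesic days is a success.

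**Illustration of equal error in both arms.** The rates are assumed. Let true success be p₁ = 30% and p₂ = 42%, with 270 per arm, and let a share m of true failures be scored as successes in each arm, so that p becomes p + (1 − p)m. Power is Φ{[Δ − 1.96√(2p̄(1−p̄)/n)] / √[(p₁(1−p₁) + p₂(1−p₂))/n]}, where Δ is the difference in rates and p̄ their mean.

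| m | Rates | Odds ratio | Power |
|---|---|---|---|
| 0 | 30.0% v 42.0% | 1.69 | 83% |
| 5% | 33.5% v 44.9% | 1.62 | 78% |
| 10% | 37.0% v 47.8% | 1.56 | 72% |
| 20% | 44.0% v 53.6% | 1.47 | 61% |

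With 40% v 52%, power goes from 80% to 62% over the same range of m; with 50% v 62%, from 80% to 65%. The documents give no value of m. The narrow band above suggests it is small for the composite.

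**The case against.** The strongest reply concerns the CM component. A reader might infer that someone with 18 or 23 treated days counts as a success at Steps 5 and 6. The documents do not support that in general, because such a participant usually fails on CM. This part of the reply stands.

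It can be added that a participant who avoids CM by having fewer than 15 headache days does not meet criterion A of Panel 4 either, and so lacks the full ICHD-3 diagnosis whatever the class mix. That is correct as far as it goes. But SAP 3.9.2 drops criterion A and labels overuse itself as MOH. On the SAP's own rule, 12 single-class triptan days are MOH and 6 + 6 mixed days are not. The inconsistency remains.

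Other points also stand in part:

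- The text in Protocol 1.1.1 is background, and the operative panels have no multi-class rule. A departure from ICHD-3 on this point therefore cannot be shown; the conflict is with Protocol 1.1.1 and the eDiary class list.
- Protocol 1.1.1 does not itself say whether days are added across classes.
- Total acute use over all six classes is tested at Steps 8 and 9, so a shift between classes is not invisible to the trial.
- The barbiturate gap may be small. Panel 4 places a barbiturate-type product beside opioids, the drug-to-class mapping is not shown, and SAP 18.5.6 reports very few North American participants.

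**Conclusion.** The concern holds for the class list. On either reading, mixed use that includes a combination analgesic or a barbiturate can reach 10 or more treated days and be scored free of MOH. For pairs within the four listed classes it is an ambiguity, not a demonstrated error.

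The standalone MOH endpoints are affected at every level of use. The composite is affected only where CM is not fulfilled, mainly at about 10 to 14 treated days or with fewer than 8 migraine days. The primary endpoint is untouched.

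A reader might also infer that the rule favours eptinezumab, or that participants move between classes after the educational intervention. The documents show neither. The rule is the same in both blinded arms, and error of equal size would pull the odds ratio towards 1. The share affected cannot be derived from the documents. The change is worth making because a stated rule gives inconsistent status in a confirmatory endpoint and the data to correct it are already collected.

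**What to change.** Reconcile Protocol 1.1.1, SAP 3.9.2 and SAP 15.1.5 in one edit:

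1. Extend the multi-class criterion to all six eDiary classes, adding combination analgesics and barbiturates.
2. State that distinct days with any listed class are counted cumulatively when two or more classes are used in the 28-day period, with the threshold at 10 days.
3. Keep the 15-day threshold for participants using non-opioid analgesics only.
4. Reconcile the single-class criteria with the 10-day opioid threshold in Panel 4, because item 1 does not capture opioid-only use.
5. Apply the rule identically at baseline and in every post-baseline period.

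If data are already unblinded, document which reading was programmed and report the corrected version as a labelled sensitivity analysis.

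The cost is SAP wording and one derivation, since drug class is recorded daily. MOH-free rates will be somewhat lower in both arms. Cumulative counting also leaves a step that should be acknowledged: 9 NSAID days plus 1 triptan day would count as overuse, while 14 NSAID days alone would not. That follows from having separate 10-day and 15-day thresholds.
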